8.5 Selection criteria

Inclusion Criteria	Non-inclusion Criteria

 - Adults aged 40-60 years with a diagnosis of type 2 diabetes mellitus (T2D) and diabetic neuropathy - Minimum duration of T2DM diagnosis: 5 years. - MNSI (Michigan Neuropathy Screening Instrument) score ≥ 2. - Both genders. - Must sign the informed consent form 	
 - Subjects with known sensitivity or hyperreactivity to cocoa or any of its components. - Pregnant women. - Subjects with neurological diseases, such as multiple sclerosis, epilepsy, or previous cerebrovascular events. - Subjects with implanted electronic devices, e.g., pacemakers. - Subjects with peripheral nerve damage in the lower extremities caused by trauma.

	
 - Subjects with a diagnosis of disc herniation below T10. - History/diagnosis of herpes zoster. - Serological diagnosis of rheumatoid arthritis or systemic lupus erythematosus. HIV/AIDS. - Venous insufficiency (C2-C6 class, asymptomatic/symptomatic according to Nicolaides CEAP classification) in lower limbs. - Clinical hypothyroidism. - Use of orthopedic equipment (e.g., prosthetics, splints, wheelchair, crutches). - Cancer diagnosis, use of oncological drugs and/or radiotherapy, or history of cancer or tumors treated with oncological drugs or radiotherapy. - Smoking, considered positive in those with a smoking index greater than 10. - History of diabetic foot (Wagner Scale 3-5) or amputation. - Presence of ulcers and open and/or extensive wounds (>2 cm) - Allodynia - Sciatic nerve root compression - Gout/Hyperuricemia
--	---

Elimination Criteria

- Subjects who modify their pharmacological treatment during the study.
- Subjects who do not attend one of the intermediate consultations
- Subjects who withdraw informed consent or decide not to continue participating in the

study

- Subjects with less than 80% adherence to cocoa supplementation
- Subjects who miss more than one consultation or do not attend the final consultation.

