Dependent	Diabetes 39 questionnaire	Questionnaire designed to measure quality of life in patients with type 1 and type 2 diabetes. (64)	Questionnaire containing 39 closed items grouped into 5 sections: energy and mobility, diabetes control, anxiety-worry, social burden and sexual functioning. Subjects rate their perception of their quality of life	No unit	Discrete quantitative

			in a global manner, with a range from 1 (minimal) to 7 (extremely severe), and the scores obtained are transformed into a scale of 0 to 100. (Appendix 7) (64)		
Confounding	Hypoglycemic drugs	Drugs that lower or regulate glucose. (65)	The use of hypoglycemic drugs will be considered when the patient is taking any drug from the following groups: Sulfonylureas (glibenclamide), biguanides (metformin), glinides, thiazolidinediones or glitazones, GLP-1 analogues, DPP4 inhibitors (sitagliptin) and alpha glucosidase inhibitors (acarbose). (66)	Present/ Absent	Qualitative nominal dichotomous

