8.7 STRATEGIC PLAN

Through an open invitation, subjects living with T2D who meet the inclusion criteria will be invited to be assessed and tested at Anáhuac México Norte University, the Kidney Specialty Center, and the Nueva Oxtotitlán Clinic (Toluca), as appropriate. The invitation will be extended, explaining the procedures, duration, and ethical issues; if the subject decides to participate, he or she will be asked to sign the informed consent letter (Annex 1). Once the subject enters the protocol, he or she will be randomized (using a random number table previously generated in a spreadsheet) to the experimental group (diet + capsules with cocoa) or the control group (diet + capsules with methylcellulose).

The study will last three months and patients will be seen on four occasions: at the beginning (baseline measurement), at the first and second month (review appointments) and at the third month (final measurement).

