Patients will be asked to attend the appointments on an empty stomach, after having urinated and defecated. Weight will be determined according to the Lohman technique, that is, without shoes and with as few clothes as possible, the individual will be placed in the center of the scale and must remain still during the measurement. (54) Waist circumference will be measured according to the proposal of the Ministry of Health of Mexico: placing the tape in a horizontal plane around the waist, taking as reference the mid-axillary line, locating the midpoint between the lower costal margin and the highest lateral edge of the iliac crest (55) and the abdominal circumference: the upper part of the hip bone and the upper part of the right iliac crest are located and the measuring tape is placed in a horizontal plane around the abdomen, at the level of the iliac crest, at the end of a normal expiration. (55) Likewise, blood pressure will be measured using a sphygmomanometer (Nebucor brand, model HL-888JA), according to the Clinical Practice Guide for the Diagnosis and Treatment of Arterial Hypertension in the first level of care (57). These evaluations will be carried out every month, until completing the three months of the duration of the study. In addition, at the beginning of the study the MNSI (Annex 3) will be applied as part of the diagnosis of DN, and both at the beginning and at the end, the TCSS (Annex 4), the questionnaire as the physical examination (51), the BEST questionnaire (Annex 5), the Bristol scale (Annex 6) and the Diabetes 39 quality of life questionnaire (Annex 7) will be applied and laboratory studies will be taken to know the biochemical parameters (triglyceridemia, HDL-c, LDL-c, glycemia,

HbA1c, TG / HDL index and neutrophil/lymphocyte ratio will be determined, as described in the table of variables.

Participants in both groups, being subjects with a cardiometabolic disease, will be nutritionally assisted, that is, all patients will be given a meal plan according to the characteristics of each one of them, calculated by the Mifflin-St. Jeor energy expenditure prediction formula (67) for subjects with obesity, while, according to the Joslin Diabetes Center, a distribution of 40-45% carbohydrates, 30-40% lipids, and 20-30% protein is suggested. (68) Two capsules will be prescribed – cocoa for the experimental group or methylcellulose for the control group – in the morning and two capsules at night.

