8.8 STATISTICAL ANALYSIS

A descriptive analysis of all dependent variables, as well as demographic variables, will be performed, expressing them as mean \pm standard deviation or, where appropriate, as median and range (min-max), according to the normality of the data; nominal variables will be expressed as frequencies. Subsequently, an intragroup inferential analysis will be carried out for weight, waist circumference, abdominal circumference and blood pressure with ANOVA for repeated samples with Tukey *post hoc*, and in case the data distribution does not meet the normality criteria, the corresponding nonparametric test will be performed (e.g.,

Friedman, followed by Dunn's *post hoc*). For biochemical analysis (glycemic and lipid profile and markers of inflammation), as well as the evaluations corresponding to diabetic peripheral and autonomic neuropathy, and quality of life, a Student's T test will be performed for dependent groups, or where appropriate, with Wilcoxon.

The intergroup comparison will be made with Student's T test for independent samples, or if applicable, with Mann-Whitney U at each measurement time. A $p < 0.05$ will be considered as statistical significance. All of the above will be carried out using version 5 of the GraphPad Prism software.

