9. ETHICAL CONSIDERATIONS

This study complies with the guidelines stipulated in the International Ethical Guidelines for Biomedical Research Involving Human Subjects, in the Declaration of Helsinki (69) and the Nuremberg Code (70), as well as the NOM-012-SSA3-2012. (71) In terms of national regulation, it adheres to the Regulations of the General Health Law on Research, within whose article 17, this protocol is considered research with greater than minimum risk due to the random method of assignment to the intervention scheme. (72) Considering the level of risk, and in accordance with the provisions of article 14, informed consent must be in writing, so each subject who participates in the study, as detailed in the Methodology section, will be informed and explained the procedures to be carried out in order to subsequently record in writing their decision to participate in an informed consent letter, in accordance with Chapter I of the General Health Law regarding the ethical aspects of research in human beings (Annex 1).

Likewise, the protocol will be submitted to the research and Bioethics committees of the Faculty of Health Sciences of the Universidad Anáhuac México Norte.

A nutrition plan will be given for the prevention or correction of obesity and to contribute to metabolic control, as indicated by the Mexican Official Standard 015-SSA2-2010 for the Prevention, Treatment and Control of Diabetes Mellitus. (76)

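### The visible protocol body plans no systematic question on adverse events or hypoglycemia and no record of why patients change drugs, stop capsules or leave, so by-arm data on these are not planned

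*Combined protocol and SAP*

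**What the plan says.** Section 8.7 schedules a baseline visit, review appointments at months 1 and 2, and a final visit at month 3. After describing weight, waist and abdominal circumference and blood pressure, it says: "These evaluations will be carried out every month, until completing the three months of the duration of the study". The TCSS, BEST, Bristol scale, Diabetes 39 and laboratory tests are planned at the start and the end only.

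The elimination criteria in 8.5 include "Subjects who modify their pharmacological treatment during the study", "Subjects with less than 80% adherence to cocoa supplementation", and "Subjects who withdraw informed consent or decide not to continue participating in the" study; missed visits also count. No instruction asks what lay behind any of these. Section 8.7.1 suspends the H-reflex test if the patient reports pain, and no variable in 8.6 captures that.

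Section 8.8 sets the scope of analysis: "A descriptive analysis of all dependent variables, as well as demographic variables, will be performed". It names no safety variable and no table of reasons for leaving.

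**The concern.** The confounder row of 8.6 lists glucose-lowering drugs that patients may be taking, among them "Sulfonylureas (glibenclamide), biguanides (metformin), glinides", and 8.5 excludes none of them. Both arms also receive a new diet; section 9 says: "A nutrition plan will be given for the prevention or correction of obesity and to contribute to metabolic control". The study's hypothesis is that cocoa improves the biochemical profile, which includes glycemia. Low-glucose episodes are therefore a reasonable thing to ask about in either arm, whether or not cocoa contributes.

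The elimination rules sharpen the problem. A patient whose physician changes a drug after an episode, or who stops the capsules because of intolerance, is removed under 8.5 and leaves only a type of exit. The patients most likely to have had a problem are those about whom least is recorded, and an analyst cannot restore the cause afterwards. Sections 2.7 and 3.2 also state that flavonoids may act without adverse effects and that the H-reflex test causes none. The planned data test the first statement only in part, and no variable is planned to test the second.

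**Working it through.** **1. Variable count.** Section 8.6 has one independent row (cocoa), one confounding row (hypoglycemic drugs) and 15 dependent rows: peripheral neuropathy, autonomic neuropathy, weight, waist, waist-to-height ratio, abdominal circumference, blood pressure, neutrophil/lymphocyte ratio, glycemia, HbA1c, triglycerides, HDL-c, LDL-c, TG/HDL and Diabetes 39. Total 1 + 1 + 15 = 17. Rows for an adverse event, a hypoglycemic episode or a cause of exit: 0. The objectives in 7.1 and the ethics text in section 9 add none.

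**2. What the existing data can show.**
- BEST (Appendix 5): bowel symptoms, mostly with a four-week recall.
- Bristol (Appendix 6): stool form.
- Diabetes 39 (Appendix 7): last-month recall. Item 15 rates how far poor sugar control affected quality of life. It does not ask whether an episode occurred or in which direction.
- Fasting glucose and HbA1c: two time points, which do not detect intermittent episodes.
- Blood pressure: monthly.
- Exits: countable by type, not by cause.

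**3. Time covered.** The plan's sample size comes first: 15.68 × 0.7056 / 0.6021 ≈ 18.4, which section 8.4 takes as 18 per group, so 36 in all. Take three months as 91 days and one month as 30 days.
- Planned follow-up: 36 × 91 = 3,276 patient-days.
- Final BEST: 36 × 28 = 1,008; 1,008 / 3,276 = 30.8%. The first 91 − 28 = 63 days (9 weeks) fall outside its window.
- Final Diabetes 39: 36 × 30 = 1,080; 1,080 / 3,276 = 33.0%.
- BEST coverage if some patients are eliminated before the final visit (rates assumed; the plan gives none): 10%, 907 days, 27.7%; 20%, 806 days, 24.6%; 30%, 706 days, 21.5%.

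These are recall windows of instruments not built for harm surveillance. They show how little of the follow-up even the nearest substitutes reach.

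**4. What systematic questions would give.** If all 18 patients in an arm were asked, the chance of seeing at least one affected patient is 1 − (1 − p)^18: 60% at p = 5%, 85% at 10% and 98% at 20% (assumed risks). Zero of 18 gives a one-sided 95% upper limit of 1 − 0.05^(1/18) = 15.3%; zero of 36 gives 8.0%. The table would be descriptive. Without systematic questioning, an absence of reports supports no such limit.

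**The case against.** A reader might infer that the trial cannot report on harm at all, or that it collects nothing bearing on the no-adverse-effects statements. The documents do not support that. Bowel symptoms, blood pressure and glycemia are measured in both arms and compared, spontaneous reports could still be noted, and exits can be counted by type. An H-reflex test cut short should leave an incomplete stored recording, though not the reason.

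Nor do the documents show that hypoglycemia is a known hazard of this regimen. They give no rate, 3.2 says that cocoa does not compromise regular medication, and the greater-than-minimum-risk label in section 9 rests on random assignment, not on a product risk.

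The monthly measurement list may also be incomplete. Drug changes and adherence under 80% must be ascertained somehow, yet 8.7 describes neither check, so the quoted sentence supports the point only by omission. The consent letter (Annex 1) is not in the public file and could contain reporting instructions. Finally, no objective in 7.1 concerns safety, and the efficacy analyses do not depend on this point.

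All of this stands and limits the claim. It does not fill the gap: nothing visible asks about events or hypoglycemia, or records why a patient left.

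**Conclusion.** The point holds for the visible protocol body. No adverse-event or hypoglycemia question is planned at any of the four visits. No cause is recorded for a drug change, capsule stop, withdrawal or H-reflex test stopped for pain. The trial therefore has no planned by-arm data on adverse events, hypoglycemia or harm-related exits. What exists is partial and falls mainly on completers: the final BEST covers at most 31% of planned patient-days, and about 22% to 28% if 30% to 10% leave before the final visit.

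This rests on 36 patients being randomised, on a 91-day follow-up, and on the consent letter not supplying what the body omits. The relevance of hypoglycemia is an inference from the co-medication, the diet and the hypothesis, without a documented rate. This is an inexpensive improvement to patient safety and to what the report can say; it does not invalidate the efficacy comparison.

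**What to change.** At months 1, 2 and 3, and at any exit contact, ask about hypoglycemia since the last visit and put one open adverse-event question. Record the cause of every elimination, capsule stop, drug change or H-reflex test stopped for pain. Add these items to 8.6, tabulate them descriptively by arm for all randomised participants in 8.8, and name the role that informs the treating physician.

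Cost: at most 36 × 3 = 108 short interviews at existing visits, plus about 4 to 11 exit contacts if 10% to 30% leave (assumed), so 112 to 119 contacts. At an assumed 3 to 10 minutes each, that is 112 × 3 = 336 minutes (5.6 hours) to 119 × 10 = 1,190 minutes (19.8 hours), plus one table and the named role's time. The real downside is that problems found may prompt more drug changes, which 8.5 turns into eliminations, and 8.4 states no dropout allowance above 18 per arm.

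Section 10 schedules recruitment for 2021 and the document was last updated in March 2025, so data collection may be over; the text does not say. In that case only the fallback applies: recover exit causes from source records and state in the report that harms were not systematically collected. That costs a record review and one sentence.

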8.7.1 H-reflex test

The H-reflex test will be performed by electrical stimulation through disposable surface electrodes (3M) connected to a bipolar constant current electrical stimulator (Digitimer DS8R). Electrophysiological signals will be recorded using surface electrodes (3M) connected to the signal acquisition and amplification system (LabChart and PowerLab 8/35, ADInstruments). The signals obtained will be sampled at 10 KHz with a band-pass filter of 0.5-500 Hz. The signals will be stored in a computer for later analysis. Once the recording and stimulation sites have been identified (see below), the subject's skin will be cleaned with an alcohol swab. Micropore® adhesive tape will be used to improve contact between the electrodes and the subject's skin. The electrodes for stimulation will be placed as follows: the active electrode (anode) at the level of the Achilles tendon, the positive electrode (cathode) above the inverted "V" between the calf muscles (gastrocnemius). The reference electrode will then be placed at the height of the heads of the gastrocnemius. The subject will be stimulated behind the knee, where the tibial nerve runs through its anatomical course. To begin the tests, the subject will be asked to indicate with his hand to the researcher when he perceives a tolerable physical sensation due to the applied current. The test will start with an intensity of 0 mA and then pulses will be given every 0.5 mV until the evoked potential (H reflex) is observed in a consistent and clearly identifiable manner based on the latency (35-45 ms). The electrical stimulus consists of the application of 1 square pulse (1 ms duration each pulse) every 10 seconds (10 pulses in total). The maximum intensity of the applied current will be in accordance with the sensitivity and tolerance of the individual in both lower limbs during the tests on the sensory and motor nerves. The applied electrical

pulse should not cause a painful sensation, but it may cause a tingling sensation. The test will be suspended if the individual reports pain or does not wish to continue with the research protocol. For the recording of the H reflex, the active electrode will be placed between the lateral malleolus and the Achilles tendon. Next, the reference electrode will be marked below it and 14 cm will be measured from the active electrode towards the middle of the calf. The "H" reflex test will be performed in two parts. The first part of the protocol consists of determining the curve of stimulus intensity vs. amplitude of the motor responses from the appearance of the "M" wave and the "H" wave, for which the electric current will be increased in steps of 0.5 μ A until the appearance of the waves. For this part, only one electric pulse (1 ms duration) will be given every 10 seconds. The intensity of the electric current that will be used for the second part of the protocol will be that whose value on the curve of amplitude of the H wave-electric current intensity reaches 60% of the maximum amplitude. This stimulation value guarantees the reproducibility and minimum variability of this wave, which also avoids muscle contraction that contaminates the electrical recording. The second part is the paired electrical stimulation test in which two electrical pulses (1 ms duration) will be produced at different frequencies between the pulses: 0.1, 1, 5 and 10 Hz. The interval between the paired pulses will be 10 s, until completing 10 series.

Electrophysiological recordings will be analyzed with Clampfit 10.0 software. The latency and amplitude of the H1 and H2 evoked potentials will be determined for each electrical pulse and at all stimulation frequencies, taking the stimulus artifact as a reference. The ratio of the amplitude of the paired H2/H1 pulses will then be determined to establish the modulation of spinal excitability. A ratio ≥ 0.6 for any stimulation frequency will be considered as an indicator of dysfunction in somatosensory processing according to Marshall et al. (18)

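### The H-reflex dysfunction cut-off of 0.6 also covers 0.1 Hz, where the paired-pulse ratio is expected to be about 1 whatever the state of spinal inhibition

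*Combined protocol and SAP*

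**What the plan says.** The second part of the H-reflex test in section 8.7.1 uses pairs of pulses that "will be produced at different frequencies between the pulses: 0.1, 1, 5 and 10 Hz". On the spacing of the pairs it says: "The interval between the paired pulses will be 10 s, until completing 10 series". No rate is set aside at the measurement stage: "The latency and amplitude of the H1 and H2 evoked potentials will be determined for each electrical pulse and at all stimulation frequencies". The H2/H1 amplitude ratio is then formed and read against one threshold: "A ratio ≥ 0.6 for any stimulation frequency will be considered as an indicator of dysfunction in somatosensory processing". Nothing exempts 0.1 Hz or names it as a reference condition.

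The same section uses a 10 s spacing for single, unpaired pulses. Of the first part it says: "For this part, only one electric pulse (1 ms duration) will be given every 10 seconds". Its general description of the stimulus is similar: "The electrical stimulus consists of the application of 1 square pulse (1 ms duration each pulse) every 10 seconds (10 pulses in total").

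Two other places describe the stimulation differently. The H-reflex row of section 8.6 defines the test as ten pulses at 10 s spacing and names no other rate. Section 2.6 describes rate-dependent depression (RDD) as measured at frequencies below 1 Hz.

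On analysis, section 8.6 lists the H-reflex indicator as a quantitative quotient (R2/R1), not as a yes/no variable. Section 8.8 says that for "the evaluations corresponding to diabetic peripheral and autonomic neuropathy, and quality of life, a Student's T test will be performed for dependent groups", or Wilcoxon, with a t test or Mann-Whitney test between groups. For categories it says only that "nominal variables will be expressed as frequencies".

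**The concern.** A paired-pulse ratio carries information about depression of the reflex only if the second pulse follows its predecessor sooner than the first pulse does. At 0.1 Hz it does not, because the gap inside a pair is the same as the gap between pairs. Calling one pulse H1 and the next H2 is then arbitrary, and a ratio near 1 is the expected result for anyone. A cut-off of 0.6 that admits this rate would read an ordinary result as dysfunction.

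RDD of the H reflex is the only measure named for the somatosensory objective in section 7.1, and 0.6 is the only threshold the plan gives for reading it. The wording has two readings. Either one rate at or above 0.6 is enough, or the same cut-off is applied to each rate separately. On the first, the label would be close to universal in both arms and at both visits and could not describe change. On the second, one of the four labels is empty.

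**Working it through.** The plan states no figure for the share of participants labelled, so there is none to reproduce. The check starts from the timing.

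**Step 1: gap within a pair (1/rate) against gap between pairs (rates and 10 s from section 8.7.1).**

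| Rate | Within-pair gap | Between-pair gap | Within ÷ between |
|---|---|---|---|
| 0.1 Hz | 10 s | 10 s | 1 |
| 1 Hz | 1 s | 10 s | 0.1 |
| 5 Hz | 0.2 s | 10 s | 0.02 |
| 10 Hz | 0.1 s | 10 s | 0.01 |

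The stated 10 s has to be the gap between pairs. Read as the gap inside a pair, it would contradict 1, 5 and 10 Hz. If it is counted from the onset of one pair to the onset of the next, the 0.1 Hz block is still a 10 s train.

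**Step 2: consequence at 0.1 Hz.** Every pulse after the first follows its predecessor by 10 s. With no drift in amplitude, H1 and H2 have the same distribution and H2/H1 has median 1. The very first pulse is the one exception, 1 of 20 in ten pairs. This step needs no assumption about variability.

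**Step 3: how often a ratio centred on 1 reaches 0.6.** The documents give no within-person variability. Assumptions: lognormal amplitudes, pulse-to-pulse CV 10–50%, s = √ln(1 + CV²), and correlation r between the two log-amplitudes of a pair.

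For one pair, P(ratio ≥ 0.6) = Φ(−ln 0.6 / (s√(2(1 − r)))), with −ln 0.6 = 0.511. Example at CV 50%, r = 0: s = √ln 1.25 = 0.472, and 0.511/(0.472 × 1.414) = 0.765, which gives 0.778.

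| CV | One pair, r = 0 | One pair, r = 0.5 |
|---|---|---|
| 10% | 0.9999 | 1.000 |
| 20% | 0.966 | 0.995 |
| 30% | 0.891 | 0.959 |
| 40% | 0.826 | 0.908 |
| 50% | 0.778 | 0.860 |

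Ten pairs are recorded, so a combined value is the more natural reading, although the plan does not say how the pairs are combined. A simulation of 400,000 participants at CV 50%, where the shares are lowest, gave:

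| Summary of ten pairs | r = 0 | r = 0.5 |
|---|---|---|
| Ratio of means | 0.989 | 0.9993 |
| Mean of ratios | 0.999 | 0.99995 |
| Median of ratios | 0.982 | 0.998 |

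**Step 4: effect on the label.** If any one rate is enough, the share labelled is at least the 0.1 Hz share. With ten pairs combined this is at least 0.982 in each arm, so the arms can differ by at most 1 − 0.982 = 0.018, or 1.8 percentage points, whatever happens at the other rates. If each rate has its own label, 1 of 4 labels is affected and the other three are untouched.

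**The case against.** The strongest reply is that nothing planned depends on the label. It is not an eligibility criterion, a section 8.6 variable or a tested outcome. Section 8.8 reports frequencies for nominal variables, but that sentence concerns the dependent and demographic variables, and the label is not among those listed. Even its appearance in a results table is an inference. This stands, and it limits the point to description and interpretation.

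The near-universal label also depends on one of two readings, and the text does not settle which applies. On the rate-by-rate reading, a careful reader would take 0.1 Hz as an undepressed reference. That stands too, but the plan does not call it a reference, and the 0.6 rule still applies to it as written.

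The numerical shares rest on an assumed CV and distribution. The timing identity does not.

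The rule is attributed to a cited study. Whether that study applied 0.6 at 0.1 Hz cannot be checked from the documents, and the argument does not use it.

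A reader might go further and infer that the H-reflex outcome as a whole is invalid, or that its between-arm comparison is lost. The documents do not support this. The tested variable is the continuous quotient, and the ratios at 1, 5 and 10 Hz have within-pair gaps at least ten times shorter than the gap between pairs. The comparison would be diluted only if 0.1 Hz were pooled into the quotient, and the plan does not say that it will be. Nor does this argument show that 0.6 is a poor cut-off at the other rates. The documents do not show how informative those rates are.

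**Conclusion.** The point holds in a limited form. At 0.1 Hz the expected ratio is about 1 by design, assuming no amplitude drift, so applying the 0.6 criterion there says nothing about spinal inhibition. If any one rate is enough, about 98–100% of participants with a recordable H reflex are labelled when ten pairs are combined. The share is lower, 78–99.99%, if a single independent pair is used. Both ranges assume lognormal amplitudes and a CV of 10–50%. If the criterion is applied rate by rate, only the 0.1 Hz label is uninformative.

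The damage is to a descriptive label. No planned test uses it, and no effect estimate or p-value changes unless 0.1 Hz enters the tested quotient. It should still be corrected, because this is the plan's only threshold for reading the sole somatosensory measure and the correction costs little.

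**What to change.** In section 8.7.1:

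- Exclude 0.1 Hz from the 0.6 criterion. It may be kept and reported as an undepressed reference.
- State whether the criterion applies to each remaining rate separately or is met by any one of them.
- State that 0.1 Hz is not pooled into the quotient tested under section 8.8. How ten pairs become one value is a separate gap that could be closed in the same sentence.

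In the same edit, reconcile three descriptions that do not agree: the H-reflex row of section 8.6 (ten pulses at 10 s spacing), section 2.6 (frequencies below 1 Hz, which of the four paired rates only 0.1 Hz meets) and the paired rates in section 8.7.1. Changing 8.7.1 alone would leave it at odds with the other two.

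Section 10 schedules the statistical analysis for January–June 2022, and the document is dated March 2025. If data have already been examined, the change should be disclosed as post hoc.

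The cost is wording in sections 2.6, 8.6 and 8.7.1, with no new recordings or participants. The downside is that one recorded frequency no longer feeds the classification.
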